# 2.3.3 Anticipated Foreseeable Risks due to Investigational Product (*IQOS*/Cigarette)

A substantial body of evidence already exists on *IQOS* and its development product, Tobacco Heating System (THS) (please refer to SPI (41)). Adverse events (AEs) reported so far seem to be mostly in line with the side effects that can be observed while using NRT. Cigarette smoking causes pulmonary, cardiovascular diseases and other serious diseases in smokers.

### 2.3.4 Unforeseeable Risks

The possibility of unforeseeable events/risks will be explained at V1. Non-expected malfunction of *IQOS* may lead to unforeseeable risks. Subjects will be informed that *IQOS* is not demonstrated yet to be less harmful than cigarettes. Mitigation will include close monitoring and medical supervision to detect any unforeseeable risks or safety signals at the earliest time possible.

## **3 STUDY OBJECTIVES**

### 3.1 **Objectives and Endpoints**

The objectives of this study are:

Objective

1. To evaluate changes in VO2max in subjects switching to *IQOS* (with and without training), continuing to smoke cigarettes (with training) and being smoking abstinent (with training)

#### Endpoint (V3, V4 and V43)

- VO2max as determined during maximal cycle ergometer exercise (expressed in absolute [mL\*min], weight-adjusted [mL\*kg\*min] and fat free weight-adjusted [mL\*kg\*min] values)
  - 2. To evaluate changes in exercise capacity in subjects switching to *IQOS* (with and without training), continuing to smoke cigarettes (with training) and being smoking abstinent (with training)

Endpoints (V3, V4 and V43)

- Exercise capacity: time to complete a pre-defined work on a cycle ergometer (min:sec)
  - 3. To assess the intensity of the exercise training in subjects participating in a training program and switching to *IQOS*, continuing to smoke cigarettes and being smoking abstinent

Endpoints (V5-V42)

- Cumulative work produced during each training session (calories and calories/kg body weight)
- Average work rate during each training session (watt and watt/kg body weight)
- Average work rate during each interval during each training session (watt and watt/kg body weight)
- Time spent at 0-50%, 50-65%, 65-75%, 75-90%, >90% of maximal work rate during each training session (min:sec)
- Average heart rate (HR) during each training session (bpm)
- Time spent at 0-50%, 50-60%, 60-70%, 70-80 % and >80 % of maximal HR during each training session (min:sec)

#### **Confidentiality Statement**
Philip Morris Products SA	Clinical Study Protocol	Confidential
P1-EXC-01-EU	Version 3.0 / 2 May 2019	Page 37 of 151

4. To evaluate changes in physiological parameters and perception of exertion and capacity in subjects switching to *IQOS* (with and without training), continuing to smoke cigarettes (with training) and being smoking abstinent (with training)

# Endpoints (V3, V43)

- Blood composition: Hemoglobin mass (g), red blood cell volume (mL), plasma volume (mL) and total blood volume (ml) as determined by CO re-breathing method
- Capillary blood lactate levels during VO2max test (mmol/L)
- Perceived rate of exertion during VO2max test (Borg Rating of Perceived Exertion (RPE) scale)

# Endpoints (V3, V4 and V43)

- Respiratory parameters at VO2max: Ventilation (L/min), respiratory rate, VCO2 (L/min), Respiratory exchange ratio (RER) (VCO2 / VO2)
- Rating of Perceived Capacity (RPC) scale
- Heart rate (bpm) and oxygen uptake (mL/min) during VO2max test
  - 5. To monitor trends of daily physical activity levels during the study in subjects switching to *IQOS* (with and without training), continuing to smoke cigarettes (with training) and being smoking abstinent (with training)

# Endpoints (from V2 until V43)

Aggregated data derived from the mobile health (mHealth) wearable for:

- Cumulative number of steps per day
- Sedentary minutes per day and % of time sedentary
- Active minutes per day and % of time active
- Very active minutes per day and % of time very active
- 6. To explore trends and changes in activity and sleep parameters through continuous measurements during the study\*

# Endpoints (from V2 until V43)

mHealth wearable measurements of steps, activity, distance, energy expenditure, sleep\* Reporting of data for this objective will be subject to a separate report(s) (not part of the Clinical Study Report [CSR]).

Data and information contained in this document are considered to constitute trade secrets and confidential commercial information, and the legal protections provided to such trade secrets and confidential information are hereby claimed under the provisions of applicable law. No part of this document may be publicly disclosed without the written consent of Philip Morris Products S.A

Philip Morris Products SA	Clinical Study Protocol	Confidential
P1-EXC-01-EU	Version 3.0 / 2 May 2019	Page 38 of 151

7. To describe changes in biological health markers in subjects switching to *IQOS* (with and without training), continuing to smoke cigarettes (with training) and being smoking abstinent (with training)

### Endpoints (V3, V14, V28 and V43)

- High density lipoprotein (HDL), low density lipoprotein (LDL) and very low density lipoprotein (VLDL) (mg/dL)
- High sensitivity C-reactive protein (hs-CRP) (mg/L)
- Growth hormone (GH) (ng/mL)
- Hemoglobin A1C (HbA1c) (%)
- Resting blood pressure (mmHg)
- Resting HR (bpm)
  - 8. To describe changes in weight, body fat and waist cirumference in subjects switching to *IQOS* (with and without training), continuing to smoke cigarettes (with training) and being smoking abstinent (with training)

Endpoints (V3, V4 and V43)

- Body fat percentage (%)
- Waist circumference (cm)

Endpoints (V3- V43)

- Body weight (kg)
  - 9. To monitor levels of exposure to CO, nitrosamines and acrylonitrile in subjects switching to *IQOS* (with and without training), continuing to smoke cigarettes (with training) and being smoking abstinent (with training)

### Endpoints

At all visits:

• Exhaled carbon monoxide (CO) (ppm)

### At V3, V4, V14, V28 and V43

- COHb% in blood (%)
- Nicotine equivalents (NEQ) in urine (adjusted for creatinine)
- Total 4-(methylnitrosamino)-1-(3-pyridyl)-1-butanol (NNAL) in urine (adjusted for creatinine)
- 2-cyanoethylmercapturic acid (CEMA) in urine (adjusted for creatinine)

### **Confidentiality Statement**

Philip Morris Products SA	Clinical Study Protocol	Confidential
P1-EXC-01-EU	Version 3.0 / 2 May 2019	Page 39 of 151

10. To describe the self-reported nicotine and tobacco containing product use over the duration of the study

Endpoints (measured daily from V2 to V43)

- Self-reported number of any nicotine/tobacco product use on a daily basis as reported in the product use diary
- Product use exposure

11. To monitor safety during the study Endpoints

- Incidence of adverse events (AEs), serious adverse events (SAEs)
- Frequency of AEs, SAEs
- Incidence of IQOS device events including malfunction/misuse
- Frequency of *IQOS* device events including malfunction/misuse
- Vital signs changes from baseline (systolic and diastolic blood pressure, pulse rate and respiratory rate)
- Physical examination changes from baseline
- Electrocardiogram (ECG) changes from baseline (heart rate, PR, QRS, QT, QTcB, QTcF intervals)
- Spirometry changes from screening visit (V1) used as baseline (FEV1, FEV1 % predicted, FVC, FVC % predicted, and FEV1/FVC)
- Cough assessment changes from baseline (VAS and three Likert scales)
- Changes from baseline in clinical chemistry, hematology, and urine analysis safety panel
- Concomitant medications
  - 12. To assess perception of health and functioning in subjects switching to *IQOS*, continuing to smoke cigarettes and being smoking abstinent \*\*

Endpoints (first interview between V2 and V3, second interview between V42 and V43)

• Changes in subjects' perception of health and functioning as determined by qualitative interviews based on the World Health Organization's International Classification of Functioning, Disability, and Health

\*\* This objective will be assessed as a sub-study with a separate section of the Informed Consent Form (ICF), and the reporting will be subject of an appendix to the main CSR.

# 4 INVESTIGATIONAL PLAN

## 4.1 Overall Study Design and Plan

This is a randomized, controlled, open-label, 4-arm parallel group study with stratification by daily cigarette consumption over the last 12 months prior to V1 as reported during V1 (i.e., 10 to 19 cigarettes or >19 cigarettes per day) and sex (Figure 2).

A sufficient number of healthy adult smokers will be screened and enrolled after checking that all eligibility criteria have been met, in order to reach 90 randomized subjects.

Smokers will be randomized as follows with a 5:5:5:3 ratio according to strata:

- 1. switch to IQOS use + participation in training program: IQOS-1 arm, 25 subjects
- 2. continue cigarette smoking + participation in training program: Cigarette arm, 25 subjects
- 3. smoking abstinence + participation in training program: SA arm, 25 subjects
- 4. switch to *IQOS* use only: *IQOS*-2 arm, 15 subjects

When 90 randomized subjects are reached, further enrollment will be stopped. Subjects already enrolled in the study will still be eligible for randomization. From randomization, subjects will be instructed to use their allocated product or stay smoking abstinent until the end of the study. Drop-outs will not be replaced.

### **Confidentiality Statement**

Philip Morris Products SA Clinical Study Protocol		Confidential
P1-EXC-01-EU	Version 3.0 / 2 May 2019	Page 41 of 151

Subjects will have serial visits at the investigational site as follows:

Screening, V1 (within 28 days prior to V2): No study-specific procedures will be performed before informed consent is obtained and the ICF has been signed. The subject will also be invited to participate in a sub-study on perception of health and functioning and will sign a separate optional section of the ICF for this part of the study. Subjects will be invited to sign a separate optional consent form for collection of samples for biobanking.

All inclusion and exclusion criteria will be assessed. A demonstration of IQOS and the mHealth wearable will be done by the site staff during the screening visit. A VO2max test will be performed as part of eligibility assessments. All eligible subjects will be invited to come to V2. Enrollment and Familiarization 1, V2 (7±1 days prior to V3): Enrollment will take place after confirmation of smoking status (urine cotinine and exhaled CO) and negative urine pregnancy test, alcohol breath test and urine drug screen. After enrollment, vital signs will be assessed and subjects will perform an exercise capacity test for the purpose of familiarization. The exercise test consists of completing a pre-defined work (calories) on a bike ergometer (1). Before leaving the investigational site the subject will receive an mHealth wearable kit and will be trained on how to handle the device. Subjects will be instructed to wear the device all the time. Subjects will also receive a diary to record the daily use of tobacco and nicotine containing products.

Between V2 and V3, subjects having signed the optional section of the ICF will have an interview (by phone or computer) on the topic of health and functioning lasting around 60 minutes.

Baseline and Randomization, V3: Baseline assessments will be performed as listed in Appendix 1. Then, 30-60 min before start of the VO2max test all subjects will smoke a cigarette (only if they are willing to). During the VO2max test at rest and at each 25 W increase, the subject's lactate levels will be determined by capillary blood sampling and the rate of perceived exertion will be assessed using the Borg RPE scale. After completing the VO2max test, the subject will rest for  $60\pm5$ min, after which the exercise capacity test will be performed. After completing exercise tests, total blood volume will be determined.

Subjects will thereafter be randomized into one of the 4 arms. Subjects randomized into *IQOS* arms will receive their *IQOS* starter kit and be trained on how to use the device. Subjects randomized into the SA arm will receive smoking abstinence support and will be allowed to use NRT upon request.

Acute effect 1, V4 (7±2 days after V3): Before the VO2 max test, vital signs, exhaled CO, weight, body-fat and waist circumference measurements will be performed. 30-60 min before start of the VO2max test subjects in cigarette and *IQOS* arms will smoke a cigarette or use a HeatStick, respectively (only if they are willing to). Subjects' VO2max, maximal heart rate and maximal work rate will be determined. After completing the VO2max test, the subject will rest for  $60\pm5$ min after which the exercise capacity test will be performed.

### **Confidentiality Statement**

Philip Morris Products SA	Philip Morris Products SA Clinical Study Protocol	
P1-EXC-01-EU	Version 3.0 / 2 May 2019	Page 42 of 151

Training program, from V5 (15±2 days after V3) until V42 (99±2 days after V3): Subjects randomized into *IQOS*-1, cigarette and SA arms will participate in 38 supervised training sessions during a 12-week period using three different training protocols (Appendix 2).

Subjects randomized to the *IQOS*-2 arm will come for visits once a week for all assessments except the training. Subjects in the *IQOS*-2 arm will consequently only attend the following visits: V5, V7, V9, V14, V16, V19, V23, V28, V30, V33, V35 and V39.

At V14 and V28 (medical visits), safety and biological health marker and exposure marker assessments will be performed for all subjects.

Before each training, the following assessments will be conducted;

- Weight
- Exhaled CO
- 30-60 min before start of the training subjects in cigarette and *IQOS* arms will smoke a cigarette or use a HeatStick, respectively (only if they are willing to).

All trainings will be performed on a bike ergometer. The training intensity will be adjusted according to the subject's resting heart rate as determined by ECG at V3 and maximal heart rate as determined at the VO2max test at V4 (acute test). The work produced, the work rate and heart rate will be recorded for each training (as described in Objective 3).

Between V42 and V43, subjects having signed the optional section of the ICF will have an interview (by phone or computer) on the topic of health and functioning lasting around 60 minutes.

Training effect, V43 (106±2 days after V3):

Before the VO2max test, biological health markers, exposure markers, vital signs, exhaled CO, weight, body-fat percentage and waist circumference measurements will be performed. Then, 30-60 min before start of the VO2max test subjects in cigarette and *IQOS* arms will smoke a cigarette or use a HeatStick, respectively (only if they are willing to). Subjects' VO2max will be determined as described for V3, including determination of lactate levels and perceived exertion rate. After completing the VO2max test, the subject will rest for  $60\pm5$ min, after which the exercise capacity test will be performed. After completing exercise tests, total blood volume will be determined.

Subjects will return the mHealth wearable, the product use diary and the *IQOS* device (if applicable).

Discharge, V44 (107±2 days after V3): Safety assessments will be conducted as listed in Appendix 1.

Safety follow-up period (from discharge at V44 or early termination plus 28 days):

After discharge on V44 or after early termination, subjects will enter a 28-day safety follow-up period during which AE/SAEs spontaneously reported by the subjects will be collected. Any

Data and information contained in this document are considered to constitute trade secrets and confidential commercial information, and the legal protections provided to such trade secrets and confidential information are hereby claimed under the provisions of applicable law. No part of this document may be publicly disclosed without the written consent of Philip Morris Products S.A

Philip Morris Products SA Clinical Study Protocol		Confidential
P1-EXC-01-EU	Version 3.0 / 2 May 2019	Page 43 of 151

non-serious AE that is ongoing at the time of discharge or early discontinuation will be followed-up by the Investigator or designee during the safety follow-up period until it has been resolved, stabilized (i.e., no worsening of the condition), or an acceptable explanation has been found (e.g., a chronic condition) or lost to follow up. The follow-up of the ongoing non-serious AEs will be done via a phone call performed until the end of the Safety follow-up period. At the end of the safety follow-up period, all ongoing non-serious AEs will be documented as "ongoing" and no further follow-up information will be sought for them by the Investigator or designee. At that point, the Investigator will assess whether the subject should be referred to his/her General Practitioner to have their ongoing AEs addressed accordingly. SAEs will be followed up by the Investigator until resolution, stabilization or the determination of a plausible explanation for them was found, regardless of the end of the safety follow-up period. All subjects discontinued from the study at any time after enrollment, will enter the 28-day safety follow-up period.

# 4.2 Rationale for Study Design

PMI is now launching a series of new clinical studies to better understand the additional benefits the reduced exposure of *IQOS* can offer to its consumers. Because of the recognized adverse effects of smoking on exercise capacity, this exploratory study is part of the program. The overall objective of the *IQOS* design is to provide an acceptable alternative to cigarettes for current, adult smokers, with substantial reduction of exposure to HPHCs by its aerosol compared to cigarette smoke.

Based on the well-known role of hemoglobin in blood oxygen transport and the formation of COHb upon CO exposure, it is assumed that when cigarette smokers switch to a smoke- and CO-free product, such as *IQOS*, their exercise capacity and response to exercise training will increase as a consequence of normalization of COHb levels and increased blood oxygenation. In order to explore this assumption, and to further assess the role of CO, smokers will be randomized to switching to *IQOS* use (*IQOS-1, IQOS-2*), continuing cigarette smoking and smoking abstinence (SA). In a previous study an effect on VO2max already after 8h of smoking abstinence has been reported (9). In this study the acute effect of switching to *IQOS* will be assessed one week after randomization. In order to assess the impact on the response to exercise training, all subjects besides the *IQOS-2* arm, will participate in a 12-week exercise training program. Whereas a reduced CO exposure in the SA-arm and the *IQOS-1* arm is thought to favorably impact response to training, continued exposure to CO in the cigarette arm would reduce the training effect in sedentary healthy smokers.

The training program designed for this study is based on previous studies demonstrating that in order to achieve improvements in cardiorespiratory fitness the optimal training frequency consists of at least 3 training sessions at a moderate intensity (~65% of maximal workload) per week (43). A bike exercise is recommended as compared to running due to the lower risk of

Data and information contained in this document are considered to constitute trade secrets and confidential commercial information, and the legal protections provided to such trade secrets and confidential information are hereby claimed under the provisions of applicable law. No part of this document may be publicly disclosed without the written consent of Philip Morris Products S.A

Philip Morris Products SA	Clinical Study Protocol	Confidential
P1-EXC-01-EU	Version 3.0 / 2 May 2019	Page 44 of 151

injuries (42, 44.) The *IQOS*-2 arm will allow to assess the impact on simply switching to a smoke-free product on  $VO_2max$  and exercise capacity.

This study is designed as an *ad libitum* study without product use restriction in order to mimic as closely as possible "real life" conditions. Subjects randomized to the cigarette and *IQOS* arms will be asked to buy their own cigarettes or HeatSticks respectively, according to their needs for the study, in order to minimize any changes in their smoking behavior. Subject randomized to the SA arm will be instructed to stay smoking abstinent until the end of the study. Subjects in the SA arm will receive smoking abstinence support and, in order to prevent relapse to cigarette smoking (i.e. CO exposure) during the intense training program, subjects will be allowed to use nicotine replacement therapy. Other drugs to aid smoking abstinence have been approved in Germany (e.g., bupropion and varenicline). However, since information on their effect on the study endpoints is sparse, their use will not be allowed in this study.

Similarly to smoking cessation (45), there is evidence that physical activity and exercise training have a favorable impact on biological health markers, such as markers for inflammation (46), lipid metabolism (47, 48) and blood glucose regulation (49). In this study the impact of switching to IQOS, alone or in combination with participation in an exercise training program, on a selected number of health markers will be assessed. It is expected that IQOS effects will be close to the ones observed in the SA arm.

Mobile health technology will be used in the study to explore the impact on switching from smoking to using *IQOS* on physical activity in daily real-world living conditions. The wearable will enable non-invasive recording of physical activity in an objective manner throughout the study.

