# 12.5 Endpoint Analysis

To evaluate changes in VO2max in subjects switching to *IQOS*, continuing to smoke cigarettes and being smoking abstinent.

A linear mixed effects model will be used to estimate the difference in VO2max between each arm (SA arm, *IQOS*-1 arm) versus cigarette arm one week after randomization (V4) and after completion of the 12-week training program (V43). The dependent variable will be the VO2max with baseline VO2max, arm, sex, age and baseline cigarette consumption as covariates. Self-reported cigarette consumption and/or *IQOS* use will be added as a covariate as well. Appropriate contrasts will be constructed to report an estimate of the VO2max and its 95% confidence intervals within each arm and also between SA arm, *IQOS*-1 arm vs cigarette arm. The comparison between SA vs *IQOS*-1 arm will be calculated as well.

To estimate the difference in  $VO_2max$  between *IQOS*-2 and other arms, the same model will be used to model the change between arms only at V43.

Other covariates may be added as deemed appropriate. The same analysis will be repeated for weight-adjusted and fat-free weight adjusted VO2max. Estimates of variability from the statistical model will be reported and may be used to power future similar studies.

To evaluate changes in exercise capacity in subjects switching to *IQOS*, continuing to smoke cigarettes and being smoking abstinent

The linear mixed effects model as described above for  $VO_2max$  will be used to estimate the difference in exercise capacity between the *IQOS*-1 or SA arm versus cigarette arm one week after randomization (V4) and after completion of the 12-week training program (V43). The dependent variable will be the time to complete the test in seconds with baseline exercise capacity (in seconds) as a covariate.

Other covariates may be added as deemed appropriate. Estimates of variability from the statistical model will be reported and may be used to power future similar studies.

To assess the intensity of the exercise training in subjects switching to *IQOS*, continuing to smoke cigarettes and being smoking abstinent

An appropriate statistical model will be used to estimate the intensity of exercise training in the various (cigarette, *IQOS*-1 and SA) arms over time. The exercise intensity will be the endpoint with baseline exercise intensity, age, visit, sex and arm as covariates. Self reported

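### After V4 no randomised contrast involving IQOS-2 isolates switching without training, so the switching-alone claim in Protocol 4.2 holds only for the one-week V4 comparison of VO2max and exercise capacity

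*Protocol*

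**What the plan says.** Protocol 4.2 gives IQOS-2 two tasks. It states that the IQOS-2 "arm will allow to assess the impact on simply switching to a smoke-free product", with VO2max and exercise capacity as outcomes. It then says that "the impact of switching to IQOS, alone or in combination with participation in an exercise training program" will be assessed on selected health markers.

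The same section says that everyone outside the IQOS-2 "arm, will participate in a 12-week exercise training program". Protocol 4.1 lists one smoking arm, and it trains: "continue cigarette smoking + participation in training program: Cigarette arm, 25 subjects". Training runs from V5 (15±2 days after V3) to V42. V4 (7±2 days) comes before it.

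The planned comparisons for IQOS-2 differ from place to place:

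- **Synopsis, endpoint analysis:** IQOS-1 versus IQOS-2 at V43, for VO2max and exercise capacity.
- **Protocol 12.5:** for IQOS-2 against the other arms on VO2max, "the same model will be used to model the change between arms only at V43". At V4 only IQOS-1 and SA are set against cigarette.
- **SAP 9.6.1.1.1, text:** at V4, IQOS-1 and IQOS-2 are pooled against cigarette. At V43, IQOS-2 is named among the arms compared with cigarette.
- **SAP Table 5:** IQOS-2 is paired only with IQOS-1 and Dual-2.
- **SAP sample code:** the LSMEANS lines that take the cigarette arm as control return IQOS-2 versus cigarette, at V43 in 9.6.1.1.1 and at V14, V28 and V43 for health markers in 9.6.1.1.6.

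Objective 7 sets the health-marker visits as V3, V14, V28 and V43.

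**The concern.** To show what switching does without training, untrained switchers must be compared with untrained smokers. From V5 the trial has the first group and not the second. It is a two-by-two layout (product by training) with one cell empty.

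The risk is one of labelling. If IQOS-2 versus cigarette is reported at V43, a training benefit in the cigarette arm counts against IQOS, and the product may look ineffective or harmful for reasons unrelated to it. If the IQOS-2 change from baseline is reported as the effect of switching, everything else that changes over about 15 weeks (106/7 = 15.1) is credited to the product. For the blood health markers there is no earlier untrained visit to fall back on.

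**Working it through.** **The plan's own figure.** The sample-size section claims a 95% CI half-width of about 10.3 mL/kg/min with 90% probability, at 20 per arm and SD 14. The formula is t(0.975, 38) × SD × √(χ²(0.90, 38)/38) × √(2/20). This gives 10.23, or 10.25 if the interval is also required to cover the true difference. The allocation is also consistent: 20/0.8 = 25, 90 × 5/18 = 25, 90 × 3/18 = 15. Precision is not the issue; identification is.

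**Cell means.** Let m be the mean change of an untrained continuing smoker by the visit in question (time, visit and repeat-test effects), s the switching effect without training, T the training effect in continuing smokers, and I the product-by-training interaction. For SA, let a be its effect without training and J its interaction with training.

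| Group at V43 | Mean change |
|---|---|
| Cigarette (trained) | m + T |
| IQOS-1 (trained) | m + s + T + I |
| SA (trained) | m + a + T + J |
| IQOS-2 (untrained) | m + s |
| Untrained smokers | m (not in the trial) |

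**Contrasts at V43:**

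- IQOS-2 − cigarette = s − T
- IQOS-2 − SA = s − T − a − J
- IQOS-1 − IQOS-2 = T + I, the training effect in IQOS users
- IQOS-1 − cigarette = s + I, the switching effect in trained subjects
- IQOS-2 change from baseline = m + s

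None equals s in general. A rank check of the design matrix agrees: s is not estimable from the V43 cells, becomes estimable if an untrained cigarette cell is added, and is also estimable if I is set to zero. Covariates cannot help, because arm fixes training completely.

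**Contrast at V4.** Nobody has trained, so T, I and J drop out. Pooled IQOS-1 + IQOS-2 minus cigarette equals s at one week and is estimable.

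**Is I = 0 tenable?** Not on the protocol's own reasoning. Section 4.2 expects lower CO exposure in the SA and IQOS-1 arms to improve the training response, and continued CO exposure to blunt it in smokers. That is an expected non-zero I. If I were as large as s, IQOS-1 − cigarette would be 2s.

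**Health markers.** V14 is at 40±2 days and V28 at 68±2 days, the ends of training weeks 4 and 8, and V43 follows training. Lipids, hs-CRP, GH and HbA1c are not drawn at V4 (Protocol Table 8). Blood pressure and pulse are taken there, as vital signs.

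**Illustration, all values assumed.** With s = 1 and T = 3 mL/kg/min, IQOS-2 − cigarette = 1 − 3 = −2. Over s from 0 to 2 and T from 2 to 6, the contrast runs from 0 − 6 = −6 to 2 − 2 = 0. It is never positive in that range only because the range keeps T at or above s. If m were as large as s, the within-arm change would be twice s.

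**The case against.** Several points on the other side are sound.

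A reader might infer that nothing planned after V4 can recover the switching effect. That goes too far. With no interaction, IQOS-1 versus cigarette equals s, and it is planned at V43, and for health markers at V14, V28 and V43. The limitation therefore rests on the interaction that Protocol 4.2 expects. Nor does that contrast use IQOS-2, the arm credited with the answer.

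A reader might also infer that the trial cannot deliver the 4.2 claim at all. The sentence gives no time horizon, and the SAP's pooled V4 comparison does isolate one-week switching for both outcomes, with IQOS-2 contributing 15 randomised subjects. That part of the claim stands.

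Nor is it true that no health marker is measured before training. All have a V3 baseline, and blood pressure and pulse are recorded at V4 and summarised by visit for safety. V4 is not a health-marker endpoint or model visit, so only the blood markers lack any untrained post-randomisation value.

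On drift, the VO2max test at V1 and the exercise-capacity familiarisation at V2 reduce learning effects, though not time and visit effects. IQOS-2 versus Dual-2 is untrained on both sides, but it is formed after randomisation from reported use and compares exclusive with partial switching.

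Finally, the study is declared descriptive, and no passage says that IQOS-2 versus cigarette will be read as the effect of switching alone. That lowers the stakes. It does not change what each contrast estimates, and a descriptive estimate still needs the right label.

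**Conclusion.** The concern holds in this form. After V4 no randomised contrast involving IQOS-2 isolates switching without training. Such an effect is identified only at V4, for VO2max and exercise capacity, about one week after randomisation. For lipids, hs-CRP, GH and HbA1c it is not identified at any visit unless product and training are assumed not to interact, against the protocol's own rationale.

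IQOS-2 versus cigarette at V43 is off by exactly the training effect in smokers. The documents do not give the size of that effect, so the figures above are illustrations and not results. The algebra treats the arms as randomised groups. The main analysis groups subjects by actual product use, which cannot supply a randomised untrained smoking group.

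The point deserves a change because the confounded comparison is planned in Protocol 12.5, in the SAP text and in the sample code, while the synopsis and SAP Table 5 leave it out. No other randomised comparison is affected.

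**What to change.** - **Protocol 4.2:** limit the switching-alone claim to the one-week V4 comparison of pooled IQOS-1 and IQOS-2 with cigarette, for VO2max and exercise capacity. State that after V4 IQOS-2 serves to estimate the added effect of training in IQOS users. Withdraw the switching-alone claim for the blood health markers.
- **Protocol 12.5:** replace the V43 comparison of IQOS-2 with the other arms by IQOS-1 versus IQOS-2, as in the synopsis and SAP Table 5, and allow IQOS-2 into the V4 comparison, as the SAP does.
- **SAP 9.6.1.1.1:** delete IQOS-2 from the arms compared with cigarette at V43.
- **SAP sample code and output:** suppress IQOS-2 versus cigarette in the V43 LSMEANS output and in the health-marker output at V14, V28 and V43, or label it as confounded by training.
- **Tables and figures:** mark IQOS-2 within-arm changes after V4 as uncontrolled description.

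This costs wording, footnotes and a few lines of code, with no new data. The sponsor gives up a claim that the design does not support. An untrained smoking arm would make the effect estimable at V43, but at 15 versus 15 and the plan's SD of 14 the half-width would be about 12.2 mL/kg/min with 90% probability. That would be a redesign, and this point does not ask for it.
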